10.4.7 Bone markers

Blood samples for exploratory bone biomarkers such as, but not limited to, collagen type 1 β -carboxytelopeptide (CTx), procollagen 1 Intact N-Terminal (P1NP), bone-specific alkaline phosphatase (B-ALP) and osteocalcin will be collected as part of clinical chemistry at Month 9 and Month 12 visits as well as at Month 3 ExFU visit. These exploratory data will not be communicated to keep the operational team and the sites blinded to treatment administration.

10.4.8 Laboratory parameters

Haematology, coagulation parameters and chemistry will be assessed at each visit during the Treatment Period, as well as at Month 1 ExFU and Month 3 ExFU visits. Fasting lipids will be assessed at Month 9, Month 12 and Month 3 ExFU visits.

E2, P4 and LH will be assessed at each visit during the treatment period, as well as at M1 ExFU and M3 ExFU visits. Serum levels of SHBG will be assessed at Month 9 and Month 12 visits.

Overnight fasting is required for Months 9, 12 and Month 3 ExFU visits.

Blood samples will be analyzed by the central laboratory. Details of blood sampling process, sample handling and shipment are described separately in a laboratory manual provided by the central laboratory. Central laboratory reference ranges will be filed in the investigator site file and in the trial master file. All laboratory results except E2, P4, LH and SHBG levels will be assessed by the Investigator/sub-Investigator. Clinically significant abnormalities compared to main study baseline status will be reported as AEs in the eCRF. E2, P4, LH and SHBG levels will not be communicated to keep the operational team and the sites blinded to treatment administration.

The laboratory parameters are listed in Appendix M.

There may be some additional laboratory parameters to be analysed as requested by the medical monitor in order to follow-up on existing abnormalities.

10.4.9 Electrocardiogram

Local 12-lead ECG readings of QTcF will be performed at each visit during the entire duration of the study.

ECGs should be performed prior to blood sampling, physical examination and vital signs.

10.4.10 Columbia-Suicide Severity Rating Scale (C-SSRS)

The C-SSRS questionnaire prospectively assesses the occurrence of treatment-emergent suicidal ideation and behavior. The questions will be administered by the site staff to the subject and completed by the site staff, using one of the following paper versions:

- either the "already enrolled subjects" C-SSRS version, dedicated to subjects who are providing answers to the C-SSRS for the first time during the study (see Appendix R).

- or the "since last study visit" C-SSRS version (see Appendix S), dedicated to subjects for whom the C-SSRS was completed at the previous study visit, for use at all remaining study visits.

10.5 LINZAGOLIX AND KP017 PLASMA LEVELS

PK blood samples will be collected from each subject at each study visit during the Treatment Period for determining linzagolix and KP017 plasma levels.

At the visits where IMP intake is at site, i.e. at Months 6, 7, 8, 9, 10 and 11 visits, PK sampling will be performed before IMP intake. The approximate time of dose administration on the four previous days and time of PK sampling will be recorded in the eCRF.

In case of early discontinuation visit, PK sampling is not required at the withdrawal visit if the subject had no IMP administration the day prior to the withdrawal visit.

Details of the blood sampling process, sample handling and shipment are described separately in a laboratory manual provided by the central laboratory.

10.6 CONCOMITANT MEDICATIONS AND THERAPIES

The Investigator will record in the appropriate section of the eCRF all concomitant medications taken by the subject during the entire study duration.

However, the use of provided/prescribed analgesics for EAP will be recorded solely in the eDiary.

10.6.1 Permitted Medicines

Any medications other than those excluded by the protocol (see section 10.6.2), which are considered necessary for the subject's welfare and/or which will not interfere with the study medication, may be given at the discretion of the Investigator.

Analgesics:

Only the analgesics provided/prescribed by Sponsor will be allowed during the study (Treatment and Follow-up Periods). Other analgesics will be prohibited. Provided/prescribed analgesics should be taken only when required for treatment of pain. Prophylactic use of analgesics will be prohibited.

Permitted opioid analgesics will be prescribed and dispensed as required according to local practice.

Subjects will be required to restrict the use of analgesics to those permitted by the protocol as listed in Table 1.

Table 1: Permitted rescue analgesics	
Analgesic class	Name and dose*
NSAID	ibuprofen 200 mg
Narcotic Analgesic	5 mg hydrocodone + 300 mg acetaminophen**

* Use of these analgesic medications should be according to the product prescribing information.

** Or local equivalent

Other:

In order to prevent or minimize possible impact on BMD, subjects will receive calcium 500 to 1000 mg and vitamin D 400 IU supplementation which they will be advised to take daily until the end of study. Intake should be recorded at each study visit in eCRF. As the interaction potential is unknown, the intake should be separated of at least 4 hours from the intake of the study drug.

If necessary, the dose of calcium or vitamin D supplementation may be reduced or discontinued at the discretion of the Investigator.

10.6.2 Prohibited Medicines

Medication listed in Appendix N will be prohibited up to Month 12.

Strong CYP3A4 inhibitors or inducers are prohibited up to end of treatment in view of the ABT (Appendix O).

Linzagolix is considered to be a weak inhibitor of CYP2C8. Substrates to CYP2C8 with a narrow therapeutic index should be administered with caution.

Hormonal contraception, including use of hormonal IUDs, must not be taken until 3 months after end of treatment.

When a prohibited medication or treatment is necessary for the subject's well-being, the Sponsor must be notified, and possible alternatives are to be discussed before administration of the prohibited medication or treatment whenever possible.

10.6.3 Non-Drug Therapies

Contraceptive use:

For subjects of childbearing potential and requiring contraception, non-hormonal contraception is required until 3 months after the end of treatment. Two forms of non-hormonal contraception will be required e.g. condom with spermicide (if in the opinion of the Investigator a woman is at risk of acquiring HIV, spermicide should be avoided; condom with diaphragm may be used). Suitable condoms with spermicide will be provided free of charge to subjects over the duration of the study.

Contraception is still required from 3 months after the end of the Treatment Period until the end of the post-treatment Follow-up Period; hormonal contraception is allowed.

10.7 SUBJECT COMPLETION AND WITHDRAWAL

10.7.1 Subject Completion

A subject will be considered as a "completer" when she has completed all study procedures/visits according to the protocol.

10.7.2 Subject Withdrawal

Subjects will be informed that they have the right to withdraw from the study at any time, without prejudice to their medical care, and that they are not obliged to state the reason(s). Any withdrawal must be fully documented in the eCRF exit form.

The Investigator may withdraw a subject at any time if this is considered to be in the subject's best interest.

In addition, the Sponsor could make a decision to temporarily or permanently discontinue the study for safety, ethical, compliance or other reasons. In this case, the subject's participation may be ended prematurely without asking for her consent.

In case of early discontinuation, the subject will be instructed to complete the relevant eDiary questionnaires as soon as possible upon treatment discontinuation.

Withdrawal during Treatment Period:

Subjects discontinuing participation in the study during the Treatment Period should undergo the procedures required at Month 12, except the DXA in case of discontinuation before Month 9 visit. These subjects will enter the 6-month Follow-Up Period and will continue daily eDiary recording for 6 months and up to Month 6 ExFU visit in order to continue to collect efficacy and safety data.

PK sampling is not required if the subject had no IMP administration the day prior to the withdrawal visit.

Withdrawal during Follow-Up Period:

Subjects discontinuing participation in the study during the Follow-Up Period should undergo the procedures required at Month 6 ExFU visit, which includes completion of all ClinRO and ePRO questionnaires, except the DXA in case of discontinuation before Month 3 ExFU visit.

10.7.2.1 Discontinuation criteria

During the course of the study, the subject may be discontinued for the following reasons:

-	Adverse Event:	Includes clinically significant new or worsening existing condition as judged by the Investigator. Document in the AE form.
-	Subject's Request:	Consent withdrawal, subject moved, schedule conflicts, etc. Specify the reason in the comment section of the eCRF Exit Form.
-	Protocol Violation:	Major protocol violation which may affect the subject's safety. Specify the protocol violation in the comment section of the eCRF Exit Form.
-	Lost to Follow-up:	Document with at least two phone calls and a certified letter requesting return receipt without response. Document in the comment section of the eCRF Exit Form.
-	Pregnancy:	Subjects who have been exposed to study treatment and who become pregnant during the Treatment Period will be immediately withdrawn from treatment. Pregnancies that have been exposed to study treatment and occurred up to Month 3 ExFU visit, or started up to 4 weeks after treatment discontinuation in case of early withdrawal will be followed up for pregnancy and neonatal outcomes at birth. Any pregnancy must be reported with the Pregnancy Surveillance Form (see section 12.6).
-	Other:	Specify in the Comments section in the eCRF Exit Form. This reason should only be used if the reason for discontinuation is not better accounted for by another category.

Discontinuation Rules:

Endometrial biopsies: in case of endometrial biopsy diagnosis being an endometrial hyperplasia of any type or worse, the subject will have to discontinue treatment and will be advised to consult for gynecological evaluation and treatment.

Serum calcium: Subjects who have a serum calcium level on treatment above 2.9 mmol/L should have calcium supplements interrupted. If serum calcium level on treatment is above 3.1 mmol/L calcium supplements **and study treatment** are to be interrupted. A repeat test of this parameter within 2 weeks under fasting conditions is to be performed. If the results of the repeat remain above

2.9 mmol/L, study treatment should definitively be discontinued and the subject should be advised to consult an endocrinologist for further evaluation.

BMD loss: subjects who experience more than 8% BMD loss or a Z-score \leq -2.5 at any site (femoral neck, hip or spine) will be discontinued from study treatment and will enter the Follow-Up Period.

Liver function tests: following the Food and Drug Administration (FDA) guidance on drug-induced liver injury (8), subjects who have an elevation of hepatic enzymes are to be withdrawn immediately from treatment if:

- ALT or AST >8xULN
- ALT or AST >5xULN for more than 2 weeks
- ALT or AST >3xULN and (TBL >2xULN or INR >1.5)

• ALT or AST >3xULN with the appearance of fatigue, nausea, vomiting, right upper quadrant pain or tenderness, fever, rash, and/or eosinophilia (>5%)

Withdrawn subjects will be followed up until hepatic parameters return to normal.

ECG: subjects who have a QTcF > 500 ms or increase > 60 ms from the highest value prior to the first dose in the main study will have to be withdrawn from study treatment and followed up until return to QTcF < 480 ms or – if not reached after 3 months of treatment cessation- be referred to a cardiologist. They will enter the 6-month Follow-Up Period and undergo the follow-up ECGs according to the schedule of events.

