5.5.1 Pharmacokinetics/Pharmacodynamics

Linzagolix was evaluated in a Phase 1 single/repeated-dose study (Study KLH1101) in which Japanese and Caucasian pre- and post-menopausal women received single doses of linzagolix from 12.5 to 700 mg and repeated once daily doses of 100 to 400 mg once daily for 7 days under fed and fasted conditions. Linzagolix was safe and well-tolerated, showed linear PK, a half-life of about 15–20 hours, and little difference between pre- and post-menopausal women or between Japanese and Caucasian women. There was a dose-dependent suppression of E2, LH and follicle-stimulating hormone (FSH).

Study 17-OBE2109-001 evaluated the tolerability and PK of a single supra-therapeutic dose of 700 mg linzagolix, and effects of therapeutic and supratherapeutic doses of linzagolix on the QTc interval (QT interval corrected for heart rate). Subjects received a 200 mg dose of linzagolix (therapeutic target exposure), a 700 mg dose of linzagolix (supratherapeutic target exposure), a 400 mg dose of moxifloxacin (positive control), and placebo with an appropriate washout. Linzagolix at 700 mg was well tolerated. A borderline effect of linzagolix on the QTc interval was identified with prolongations exceeding the threshold of concern by less than 2 msec. The categorical data for QTc showed no values greater than 480 msec and no changes greater than 30 msec following administration of the supratherapeutic and therapeutic doses. Thus, based on the magnitude of the QTc prolongation, the observed effects are not considered to be clinically significant.

The open-label study, KLH1103, assessed the absorption, metabolism, and excretion of linzagolix in 6 women of non-childbearing potential. Linzagolix was the predominant component in plasma and all plasma metabolites were present at less than 10% of the total drug related exposure. Similarly, unchanged linzagolix was also a major component in urine and feces. Linzagolix was eliminated in urine (52%) and, to a lesser extent, in feces (38%).

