10.2.2.2 Study visit: Month 3 Extension FU (Month 3 ExFU)

Month 3 ExFU visit should be scheduled on Day 421 ± 7 days after Day 1 (or 84 days ± 7 days after last IMP intake for early discontinued subjects).

The following tests and evaluations will be performed at Month 3 ExFU Visit:

- eDiary completion compliance check
- ePRO and ClinRO completion, ideally before any other procedures or assessments: EHP-30, EQ-5D-5L, PROMIS, mPGIS, PPGIC, HRUQ, HRPQ (mPGIS and PPGIC must be completed last)
- Concomitant treatments recording
- AE recording
- Completion of the paper C-SSRS questionnaire (version for "already enrolled subjects" (see Appendix R) for patients responding to the C-SSRS for the first time during the study, or version "since last study visit" (see Appendix S) for patients for whom the C-SSRS was completed at the previous study visit)
- ECG
- Physical examination, including weight recording
- Vital signs (BP and heart rate)
- Urine pregnancy test and contraception counselling
- Gynecological examination
- Manual breast examination (by palpation)
- TVUS of uterus
- Urinary protein dipstick
- Fasting (overnight) blood samples for haematology, coagulation parameters, chemistry, lipids, hormones (E2, LH and P4) and bone markers. For subjects who do not resume menses by the Month 3 ExFU visit, an FSH test should be performed at a local laboratory and the subject should be advised to consult for gynaecological evaluation.
- Endometrial biopsy only if diagnosis at preceding biopsy was different than "benign endometrium" or if no endometrial biopsy was done at Month 12 nor at any visit after Month 12 (see section 10.4.5).
- Prescribe/dispense permitted analgesics as rescue medication
- Dispense calcium and vitamin D supplementation

10.2.2.3 Study visit: Month 6 Extension FU (Month 6 ExFU) – End of Follow-up visit

Month 6 ExFU visit should be scheduled on Day 505 ± 7 days after Day 1 (or 168 days ± 7 days after last IMP intake for early discontinued subjects).

The following evaluations and tests will be performed at Month 6 ExFU Visit:

- eDiary completion compliance check
- ePRO and ClinRO completion, ideally before any other procedures or assessments: EHP-30, EQ-5D-5L, PROMIS, mPGIS, PPGIC, HRUQ, HRPQ (mPGIS and PPGIC must be completed last)
- Collection and deactivation of eDiary
- Concomitant treatments recording
- AE recording

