12.1.2 Abnormal laboratory findings and other objective measurements

Abnormal laboratory findings and other objective measurements (e.g. vital signs) must be reported as an AE only if assessed by the Investigator as "clinically significant" e.g. meeting at least one of the following conditions:

- 1. The abnormality suggests a disease and/or organ toxicity AND this abnormality was not present at the main study screening visit or is assessed as having evolved since this visit.
- 2. The abnormality is a Serious Adverse Event.
- 3. The abnormality results in discontinuation of the IMP.
- 4. The abnormality requires medical intervention or concomitant therapy.

The Investigator must initial and date each laboratory report/eCRF page and note directly on the report/eCRF page whether or not each out-of-range laboratory result is clinically significant. The outcome of this assessment will be reported using an AE or SAE form, as appropriate.

When reporting an abnormal finding for laboratory parameters or other objective measurements on the AE page of the eCRF, a clinical diagnosis should be recorded rather than the abnormal value itself, if available (for example, "anaemia" rather than "decreased red blood cell count").

For all of these AEs, whether or not related to the treatment, the laboratory test(s) will be followed-up as appropriate.

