12.5 REPORTING PERIOD

AEs are collected on an ongoing basis from the day of signed informed consent. All new AEs and updates on all ongoing AEs or AEs with an unknown outcome, must be recorded up to the Month 6 ExFU visit.

A last batch of queries will be sent after last study visit if remaining ongoing/unknown outcomes of reported AEs are pending. After the last batch of queries with all collected data has been fully processed, eCRF and database will no longer be updated. Only SAEs and medically relevant ongoing/unknown outcome AEs will be followed-up until resolution or stabilization, under Voisin Consulting responsibility.

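### The QTcF recovery target ignores the 60 ms trigger, so a woman stopped for a rise that leaves her below 480 ms can never reach the mandatory cardiology referral

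*Protocol*

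**What the plan says.** The ECG paragraph of Protocol 10.7.2.1 has two alternative triggers for stopping treatment: an absolute QTcF above 500 ms, or an "increase > 60 ms from the highest value prior to the first dose in the main study". Women who meet either one "will have to be withdrawn from study treatment and followed up until return to QTcF < 480 ms". The only escalation beyond that target is a referral clause, which reads: "if not reached after 3 months of treatment cessation- be referred to a cardiologist". The paragraph then adds: "They will enter the 6-month Follow-Up Period and undergo the follow-up ECGs according to the schedule of events". SAP 2.3.1 restates the rule with the same two triggers, the same 480 ms target and the same 3-month referral.

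The follow-up ECGs are at Month 1, Month 3 and Month 6 ExFU (Protocol 10.2.2, 10.4.9 and Appendix B). For women who stop early, the Month 3 ExFU visit is placed "84 days ± 7 days after last IMP intake for early discontinued subjects". Neither document states a recovery or referral criterion relative to the pre-dose value.

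**The concern.** One trigger is absolute and the other is relative to the woman's own pre-dose value, but recovery is judged only on the absolute scale. A woman can therefore be stopped because her QTcF rose too far and be classed as recovered at the same moment, with the rise unchanged.

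The referral is the rule's only mandatory escalation step, and it exists for prolongation that persists off drug. Cardiac safety including QT prolongation is a stated safety objective (Protocol 6.2), and the sponsor treats a rise above 60 ms as sufficient reason both to end treatment and to refuse entry to the extension (Protocol 9.2.2, criterion 5c). What is at stake is the care of an individual woman. No estimate or analysis depends on this point.

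**Working it through.** **Inputs**, all from Protocol 10.7.2.1: stop if Q > 500 or Q − b > 60, where Q is QTcF in ms and b is the highest value before the first main-study dose. The recovery target is Q < 480. Referral follows if the target is not reached 3 months after stopping. The plan states no figure of its own for this rule, so there is none to reproduce.

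**When the target is already met at the stop ECG.** The second trigger fires at Q > b + 60. The target is met at that same ECG when

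b + 60 < Q < 480.

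This interval is non-empty only if b + 60 < 480, that is, b < 420 ms. In whole milliseconds it needs b ≤ 418, because b = 419 gives a first stop value of 480.

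**When the referral fires.** Suppose the stop value persists to 3 months. Referral requires Q ≥ 480, which is false for every value in that interval.

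**Recovery if both criteria were required**: Q < 480 and Q − b ≤ 60. The highest whole-ms value that counts as recovered is min(b + 60, 479).

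| b (ms) | Stop values in the gap (ms) | Rise (ms) | Whole-ms values in the gap | Referred now if persistent | Referred with both criteria | Highest value counted as recovered: now → both |
|---|---|---|---|---|---|---|
| 380 | 441–479 | +61 to +99 | 39 | 0 | 39 | 479 → 440 |
| 400 | 461–479 | +61 to +79 | 19 | 0 | 19 | 479 → 460 |
| 410 | 471–479 | +61 to +69 | 9 | 0 | 9 | 479 → 470 |
| 415 | 476–479 | +61 to +64 | 4 | 0 | 4 | 479 → 475 |
| 418 | 479 | +61 | 1 | 0 | 1 | 479 → 478 |
| 419 or more | none | – | 0 | – | – | 479 → 479 |

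**Example.** b = 400 and stop value 465, a rise of 65 ms. At Month 3 ExFU she is still at 465. Since 465 < 480, the target counts as reached and no referral follows, although the rise that ended treatment is unchanged.

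**Where the rule works.** After a stop above 500 ms, or after a rise above 60 ms with a stop value of 480 ms or more, the target is not met at the stop ECG, so the referral can still be triggered.

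**The other reading of *return to*.** One could say the target does not apply to a woman who was never at 480 ms or above. She then has no recovery endpoint at all, and the referral still has nothing to trigger it.

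**The case against.** The strongest reply is that this matters little, for five reasons.

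- **Rarity.** Three things must coincide: a rise above 60 ms over the *highest* pre-dose value, a stop value below 480 ms, and persistence for 3 months off drug. In the QT study, "The categorical data for QTc showed no values greater than 480 msec and no changes greater than 30 msec", including at 700 mg. That study gave single doses, so it makes the event unlikely without excluding it.
- **Persistence is unlikely to be a drug effect.** The half-life is about 15–20 hours (Protocol 5.5.1). At 84 days, 84 × 24 = 2016 hours have passed, which is 2016/20 ≈ 101 to 2016/15 ≈ 134 half-lives. This stands. However, a rise that outlasts the drug still has no explanation, and the existing referral clause is written for prolongation that continues after stopping.
- **Other safeguards.** Protocol 12.1.2 makes an abnormality a reportable adverse event if "The abnormality results in discontinuation of the IMP". Under 12.5, "Only SAEs and medically relevant ongoing/unknown outcome AEs will be followed-up until resolution or stabilization". The data monitoring committee reviews ECG parameters (5.7), SAP 4.8.6 summarises change from the highest pre-dose value, and an investigator may always refer. All of this means that observation is not lost. None of it requires a referral or defines recovery of the rise. The committee's role is advisory (14.5), and a steady +65 ms could itself pass as stabilization.
- **It may be a deliberate choice:** a sensitive stopping trigger with an absolute threshold for referral. The liver rule carries no specialist referral at all. But the liver rule follows women until their values are normal, and the calcium rule sends a woman to an endocrinologist on the same repeat value that ends treatment. The ECG rule has a relative trigger with no relative recovery test, and the protocol gives no reason for that.
- **Early termination.** SAP 1.2 records that the study stopped early with far fewer subjects than planned. This limits what a change can achieve in this trial. It does not make the written rule right.

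These points reduce the weight of the concern. They do not alter the logic or the arithmetic.

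**Conclusion.** The concern holds. The gap is confined to women stopped under the relative trigger with a stop value below 480 ms, which requires a highest pre-dose QTcF below 420 ms. Within that group the mandatory referral cannot follow from a persistent rise, whatever its size up to the 480 ms limit.

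The conclusion rests on reading the rule as written and on the stop value persisting to 3 months. The number of women affected cannot be estimated, because neither document gives a pre-dose QTcF distribution, and it is probably small. No endpoint or analysis is affected. This is a correction the plan should make to a participant-safety rule; it does not threaten the trial's conclusions.

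**What to change.** In Protocol 10.7.2.1, define recovery by both criteria, whichever trigger fired: follow up until QTcF is below 480 ms **and** the increase over the highest pre-dose value is no longer above 60 ms. Refer to a cardiologist if either is not reached 3 months after stopping.

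Keep the absolute target for everyone. A woman at 435 ms pre-dose who stops at 498 ms (+63) would be back within 60 ms at 495 ms, and she should still be followed to below 480 ms: min(435 + 60, 479) = 479.

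The 60 ms limit reuses the sponsor's own threshold. It is lenient: with b = 400, a fall from 465 to 460 ms would count as recovered. The clinical team may prefer a tighter limit.

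Align the restated rule in SAP 2.3.1 for consistency; no analysis changes. The cost is one protocol clause and possibly a few more cardiology referrals. The Month 3 ExFU ECG is already scheduled at the right time, and the pre-dose reference is already needed to apply the trigger.
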